#### Facebook Protocol

A Facebook account will be opened under the study name '*Libre del Cigarrillo*.' The profile will contain the study and Moffitt Cancer Center logo, along with a paragraph briefly describing the study. Facebook searches will be initiated using the participant's first and last names. If the first and last names result in a match, we will attempt to further verify we have identified the correct individual by confirming 'current city', 'age', or 'email address'. When we are confident that we have identified the right individual, we will use the internal messaging system of the Facebook platform. An initial message will be sent to the individual asking if they are participating in *Libre del Cigarrillo*. The message will emphasize that we have exhausted all other means of contact, provide our telephone number and email address, and request that the individual contact us or reply via the internal messaging system regarding their willingness to update their contact information and continue their participation in the study. The message will apologize in advance for possibly contacting the wrong individual. If this was the case, we will additionally request that they simply reply with this respect to ensure they are not to be contacted in the future. If the user does not reply, another message will be sent 14 days later.

**D3.4.2. Outcome Variables.** At each assessment point we will calculate 7-day point- prevalence abstinence rates. Point-prevalence measures are best for capturing the dynamic nature of cessation, maintenance, and relapse. Continuous abstinence is not feasible because quit dates will be highly variable across participants, and also because one goal of the intervention is to encourage lapsers to quit again (recycle). We need our outcome measures to reflect these changes in smoking status over time. We will also compare groups on continuous measures such as current smoking rate (cigarettes/day), months of smoking during the follow- up period, length of current abstinence period, and latency from quit date to relapse. Data will be analyzed following multiple imputation (see below). *Finally, we will calculate the cost per participant of each intervention, and then incremental cost-effectiveness ratios, using Usual Care as the reference, to determine the cost per quitter. These statistics will facilitate economic comparisons with other cessation interventions.*

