### **D3.7. Data Management and Analysis**

**D3.7.1. Data Management.** Participant recruitment and contact information will be input through screens created by the Data Systems Team within Moffitt's Research Computing Support Group (Research IT) and will be subject to computerized range and consistency checks. The data will then populate an Access database, which will also be created and maintained by Research IT. This process will be supervised jointly by the PI and Study Data Manager/Biostatistician. Paper-and-pencils surveys will be entered into database files with computerized range and consistency checks. Online surveys will have range checks built into the survey items, as appropriate. The survey databases will be converted on a monthly basis to an analysis database. This analysis database and SAS version 9.4 (SAS Institute, Cary, NC) will be used by the statistician who will provide the PIs with reports and summaries on a regular basis and perform the final analyses.

**D3.7.2. Sample Size and Study Power Analysis.** The primary statistical analyses will assess the efficacy of the full intervention (SS-SP) in producing smoking cessation compared to Usual Care (UC) in two ways: (1) across all 4 follow-ups using generalized estimating equations (GEE), and (2) at the 24-month follow-up using logistic regression. The estimated 7-day point prevalence abstinence rates for this study were based on the cessation study (C1.2.3, Table 1) with an adjustment of 0.625 standard error units to decrease group differences. For the four follow-ups, the estimated abstinent rates are 12.3%, 15.2%, 19.1%, & 19.8% in the UC condition and 15.2%, 23.0%, 26.9%, & 28.8% in the SS-SP condition. Power was targeted to be  $> .80$  with alpha=.05 and a 2-sided test. Using GEESIZE version 3.1 (Rochon, 1998; Dahmen 2004) with an AR(1) working correlation structure and coefficient of 0.7, sample size was estimated at 322/group for the GEE analyses. For the logistic regression at 24 months, sample size was estimated at 365/group. All analyses will be completed following multiple imputation to manage missing data (below). Therefore, no adjustments of

enrollment size will be needed to account for attrition. The final sample size for analyses was rounded up to 370 per group. An additional 500 participants will be recruited from the state of Florida.

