We initially planned to enroll 1240 individuals, 740 nationally and 500 in Florida. However, due to higher-than-expected attrition, we are increasing our overall sample size to 1400 individuals, 850 nationally and 550 in Florida.

**D3.7.3. Data Analysis Overview.** Analyses will be conducted with SAS version 9.4 and Mplus Version 7 (Muthén & Muthén, 2008). Frequency distributions and contingency table analyses will be used as a point of departure for more advanced analyses. Group differences in baseline measures will be assessed and any variable that exhibits a significant group difference will be incorporated into the primary analyses.

To manage missing data, multiple imputation under the Missing at Random assumption will be applied using a Markov Chain Monte Carlo method (Schafer, 1997) via PROC MI in SAS, given the expected large number of non-monotonic missing data patterns and the expected large number of auxiliary variables (e.g., baseline measures that predict smoking status at follow-up) to be determined by preliminary analyses. A post hoc approach (Rubin, 1987) will address the influence of Missing Not at Random (MNAR) on smoking status (i.e., missing is due to smoking). Sensitivity analyses will be performed by comparing results from different multiple imputation data sets that were generated using different levels of MNAR influence.

**D3.7.4. Analytic Plan for Addressing Specific Aims.** All analyses will be performed on complete data sets following multiple imputation using all 1400 participants.

**Specific Aims 1.** All analyses will be performed on complete data sets following multiple imputation. Generalized estimating equations (GEE) will be used to fit population-averaged models of the longitudinally measured 7-day point prevalence, with the main covariates of intervention condition (UC vs. SS-SP), time (months from baseline), and the interaction of condition and time. The GEE analysis will allow for assessment of changes in abstinent rates over time and group differences in changes. Logistic regression will be used to assess condition differences at the 24-month (final) follow-up, which is 6 months after the SS-SP intervention. In both the GEE models and logistic regression, potential confounding variables (e.g., group differences on demographic variable) that appear despite randomization will be included.

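### Latency from quit date to relapse is defined only for participants who quit after randomisation, so the planned between-arm comparison is not a randomised one and multiple imputation cannot make it so

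*Combined protocol and SAP*

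**What the plan says.** D3.4.2 (Outcome Variables) makes 7-day point prevalence the outcome at each assessment and then adds: "We will also compare groups on continuous measures such as current smoking rate (cigarettes/day". The list continues with months of smoking during follow-up and ends with "length of current abstinence period, and latency from quit date to relapse". The section on Primary and Secondary Outcome Measures in the data safety and monitoring plan repeats the list.

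D3.4.2 also explains why a continuous-abstinence outcome was rejected: "Continuous abstinence is not feasible because quit dates will be highly variable across participants". Its second reason is that participants who lapse are encouraged to quit again.

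On the analysis set, D3.4.2 says that data are analysed after multiple imputation, and D3.7.4 says: "All analyses will be performed on complete data sets following multiple imputation using all 1400 participants". The models in D3.7.4 (GEE and logistic regression) concern 7-day point prevalence and its moderators.

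For the two abstinence-duration measures, the documents do not state:

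- who is analysed;
- what value a never-quitter or current smoker receives;
- which quit attempt counts;
- how quitters who have not relapsed are censored;
- which test is used.

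**The concern.** Participants must be smokers at entry: the baseline rules in D3.2 remove anyone who has not smoked in the past week. Nobody therefore has a latency to relapse when randomised. A participant acquires one only by quitting later, and has an observed value only after also relapsing.

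Randomisation makes the 700 and 700 comparable. It does not make the quitters in one arm comparable with the quitters in the other when the intervention is intended to change who quits. A difference in latency then mixes any effect on staying quit with a difference in the kind of person who quit and in how long each could be observed afterwards.

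The two reasons D3.4.2 gives against continuous abstinence, variable quit dates and repeated attempts, apply equally to latency from a quit date. Yet latency is kept, with no rule for the index attempt.

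At stake is a secondary result on maintenance that looks like a randomised comparison and is not one.

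**Working it through.** **1. The plan's own figure.** The documents give no figure for latency or abstinence length. The nearest is the 24-month sample size of 365 per group (D3.7.2), for 19.8% vs 28.8% "with alpha=.05 and a 2-sided test" and power above .80. The unpooled formula gives (0.198×0.802 + 0.288×0.712) × (1.960 + 0.842)² / 0.090² = 353. The pooled version gives 356 and the Wald log-odds-ratio version 360. All are within about 3% of 365, so the planning rates can be taken as read.

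**2. The arms are expected to differ in who is abstinent.** The planned rates at 6, 12, 18 and 24 months are "12.3%, 15.2%, 19.1%, & 19.8% in the UC condition and 15.2%, 23.0%, 26.9%, & 28.8% in the SS-SP condition". At 24 months that is 0.198×700 = 138.6, about 139 people, vs 0.288×700 = 201.6, about 202. Abstainers in excess of the UC rate make up (0.288 − 0.198)/0.288 = 31% of SS-SP abstainers. These are abstinence rates. The documents do not give the share who ever quit, or who quit and relapsed.

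**3. The sign for latency depends on an unknown.** Let q0 and q1 be the shares who ever quit in UC and SS-SP. Suppose everyone who would quit under UC would also quit under SS-SP, with the same mean latency L in both arms, and let the extra SS-SP quitters have mean m. Ignoring censoring:

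- quitters-only difference (SS-SP minus UC) = s(m − L), with s = (q1 − q0)/q1;
- difference in mean time abstinent over all randomised, never-quitters at 0 = (q1 − q0)m.

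With purely assumed values q0 = 40%, q1 = 50%, L = 6 months, s is 0.20:

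- m = 3: quitters-only −0.6 month; all randomised +0.3
- m = 6: quitters-only 0; all randomised +0.6
- m = 9: quitters-only +0.6; all randomised +0.9

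In all three cases nobody's latency is changed by the intervention. The quitters-only difference moves only with m, on which the documents are silent.

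**4. Length of current abstinence at 24 months.** Assume, for illustration, that nobody relapses and that each rise in the planned rate is made up of quits at the interval midpoint. Abstinence at month 24 is then 21, 15, 9 or 3 months.

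- UC increments 12.3, 2.9, 3.9, 0.7 points: 12.3×21 + 2.9×15 + 3.9×9 + 0.7×3 = 339.0. Abstainers only: 339.0/19.8 = 17.1 months. All randomised, smokers at 0: 339.0/100 = 3.4.
- SS-SP increments 15.2, 7.8, 3.9, 1.9 points: 15.2×21 + 7.8×15 + 3.9×9 + 1.9×3 = 477.0. Abstainers only: 477.0/28.8 = 16.6 months. All randomised: 477.0/100 = 4.8.

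The abstainers-only difference is 16.56 − 17.12 = −0.6 month (favours UC). The all-randomised difference is 4.77 − 3.39 = +1.4 months (favours SS-SP). Placing quits at the start or end of each interval adds or subtracts 3 months for every abstainer. That leaves the first difference at −0.6 and moves the second to 1.38 ± 0.09×3, that is 1.1 to 1.7. The signs differ because the planned gap widens from 2.9 points at 6 months to 9.0 at 24, so SS-SP's extra quits come later and have had less time to accumulate.

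**5. Why imputation does not help.** Multiple imputation under Missing at Random fills in values that exist but were not observed. A never-quitter has no latency to recover, and a quitter still abstinent has one known only to exceed the time observed. Imputing the first invents data; treating the second as ordinary missing data discards what is known.

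**The case against.** The strongest reply is that the plan never says it will compare means among relapsed quitters. It names no subset and no test, does not exclude time-to-event methods, and says that analyses use all 1400. Latency is also the last item in an open-ended list that already contains an all-randomised measure, months of smoking. On this view the gap is only missing detail.

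Part of this stands. A reader might infer that a quitters-only comparison of means is planned; the documents do not say so. But specification alone would not cure the problem. Under any reading latency needs a quit after entry, so a between-arm test rests either on selected subsets or on invented values. A survival analysis from the quit date handles censoring but not the selection.

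Other stronger readings also go beyond the documents:

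- **That the bias would favour UC.** This needs the extra quitters to relapse sooner, which the documents neither support nor exclude. The materials are designed for maintenance as well as cessation, and the earlier booklets reduced relapse (12% vs 35%; 22% vs 32%, D1.2). Those trials concerned people who had already quit, so they do not settle the matter for people who quit after entry.
- **That a latency deficit can be sized from the 24-month rates.** People abstinent at 24 months have not relapsed from that quit, so those rates do not count people with an observed latency.
- **That Hypothesis 1 is at risk.** It concerns abstinence rates through 24 months and is tested on point prevalence only.
- **That length of current abstinence is equally flawed.** It is sound if current smokers are given 0; the plan simply has no such rule.

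**Conclusion.** The concern holds for latency to relapse. As listed, the between-arm comparison is not a randomised treatment effect, and the statement about all 1400 participants does not make it one. That conclusion rests on the definition of the measure and on the plan's expectation that abstinence differs by arm, not on any assumed latency. The direction and size of the bias cannot be known from the documents; it could favour either arm.

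For length of current abstinence the concern is conditional on analysis among abstainers. The contrast of −0.6 with +1.4 months is an illustration that assumes no relapse and a common quit point within each interval. It shows that a reversal is possible under the plan's own rates, not that it will happen.

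The primary GEE and logistic analyses, the test of Hypothesis 1, the sample size and months of smoking are unaffected. This is a worthwhile, inexpensive improvement to the secondary outcomes.

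**What to change.** Amend D3.4.2 and the matching text under Primary and Secondary Outcome Measures, before outcome data are analysed:

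- Make months of smoking during follow-up, already listed, the main continuous comparison, on all randomised participants.
- Code length of current abstinence as 0 for current smokers and compare it on all randomised participants.
- Report latency to relapse among quitters descriptively by arm, without a between-arm test. State the index quit attempt and how those still abstinent are censored, and say that this is not a randomised comparison.
- State that undefined latencies are not imputed.

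Counting never-quitters as relapsed at time zero is not a good substitute. It mixes time origins and largely repeats the cessation comparison.

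The cost is a few lines of text. Follow-up questionnaires already ask about tobacco use since the previous contact. The price is that the all-randomised measures mix quitting with staying quit, and the trial gives up a formal test of latency.

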#### D3.5. Study Timeline

Month	Activity
1 – 3	Hire and train staff; build database program; work with CAB and CAP to develop targeted recruitment plan and create advertising copy; translate assessment instruments; print intervention materials.
4 – 23	Accrue sample and begin distribution of interventions and follow-up assessments.
24 – 53	Continue Follow-up Assessments and prepare mid-term reports.
54 – 60	Complete final data analysis and prepare reports.

#### D3.6. Design Considerations

In this section we briefly address our rationale for a few important study-design decisions.

**Should biochemical verification be employed?** The decision regarding inclusion of biochemical verification (e.g., saliva, serum, or urine cotinine; breath carbon monoxide) of self- reported smoking status is complex (Benowitz et al., 2002). Considering the low-intensity nature of the intervention, that assessments will be done by mail/internet, and there should be little differential in social-desirability demand across conditions, we concluded, consistent with Benowitz et al. (2002) and Velicer et al. (1992) that bio-verification of the full sample is not warranted. Moreover, the cost of bioverification for a study of this size and geographic distribution would be prohibitive. In two prior studies, we conducted unannounced CO tests of 64 participants who self-reported abstinence at follow-up and who resided within 50-75 miles of our laboratory. Findings were consistent with self-reports for all but one participant. *We will use this same*

strategy to collect CO and saliva from a sample of participants residing within 75 miles at the 12 and 24 month follow-up points. In the unlikely possibility that we find nontrivial disconfirmation rates, we will use the data to adjust our outcome estimates.

**Should pharmacotherapy use be an exclusion criterion?** Excluding smokers who report using any pharmacotherapy would allow for a “cleaner” test of the self-help interventions per se. However, we ultimately decided against this exclusion criterion for the following reasons:

(1) It would reduce the ecological validity of the study, because pharmacotherapy is readily available to smokers and is likely to be used by many smokers in the population to which we wish to generalize; in fact, the *Stop Smoking for Good* booklets and supportive pamphlets themselves discuss pharmacotherapy options. (2) It would cause us to reject or drop a significant proportion of participants, necessitating a much larger initial sample size and a study of longer duration. Instead, we will assess pharmacotherapy use (as well as electronic nicotine delivery systems [i.e., e-cigarettes]) at each assessment and we will examine their contribution statistically.

#### **C.7.1. Should materials be distributed only via the Internet or mobile modality?**

We propose to give participants an option to receive intervention materials electronically (via emailed link) in addition to printed “hard copies” delivered by the US Postal Service. Internet- only distribution would have the advantage of reduced cost and easier eventual dissemination (c.f., Marcus et al., 2007). However, there are also advantages of tangible, printed intervention materials (Curry et al., 2003), and this was the modality that showed substantial efficacy in our prior studies, including the English-language version of the proposed intervention. A written intervention is also particularly useful for low-income individuals who may experience barriers to access of technological modalities. Rather than introducing additional variation, we feel that priority should be given to testing the booklets in their present form. Nevertheless, we will track use of the Internet option and include it as an exploratory moderator variable in analyses. We will collect metadata regarding use of the internet-based documents, namely how many times the link was accessed, and whether the electronic booklet(s) were downloaded, which will allow us to document their use and acceptability. We will also collect evaluations and preferences regarding internet distribution at follow-up to test as potential moderators or mediators of treatment effects. This information should assist us in deciding whether to transition fully to internet-based or mobile content (i.e., smart-phone/tablet apps) distribution in the future.

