### **D3. Methods**

#### **D3.1. Design Overview.** *A randomized 2-arm design, with 700 smokers recruited into each of*

the conditions will be used to test the efficacy of our Spanish-language smoking cessation intervention. The 2 conditions are: (1) Usual care (UC), which will comprise a single, Spanish-language, smoking cessation booklet developed by NCI; and (2) the Stop Smoking for Good Intervention in Spanish (SS-SP), comprising a series of 11 booklets distributed over 18 months, plus additional monthly contacts via 9 supportive pamphlets. Assessments for both groups will occur at six-month intervals, through 24 months. An overview of the design and the timing of intervention components and assessments are depicted in Table 2. All conversations with participants, informed consent, intervention materials, and assessment instruments will be in Spanish.

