### **D3.3. Study Arms**

*In this section, we describe the rationale and form of the two intervention conditions.*

Note that in addition to hard copies of the intervention materials, participants in both conditions will have the option to also receive electronic versions via a link to a website managed by Moffitt Cancer Center's Survey Methods Core.

**D3.3.1. Stop Smoking for Good Intervention in Spanish (SS-SP).** This condition will comprise the 11 *Stop Smoking for Good* booklets and 9 supportive *My Story* pamphlets transcreated for Spanish speaking smokers to be delivered over 18 months (see Table 2).

Consistent with the recommendations of the USPHS Clinical Practice Guidelines (Fiore et al., 2008), our prior formative work with Hispanic/Latino smokers and Hispanic/Latino health care providers ([name] et al., 2011a; 2011b; Bejarano et al., 2013) identified high degrees of interest and enthusiasm for self-help smoking intervention materials to be available in Spanish. Additionally, a reoccurring emergent theme among Hispanic/Latino participants was a desire for some form of personal contact to be provided along with the booklets. To satisfy this identified need, while maintaining dissemination and reach potential, we have added a single, brief telephone contact to this condition. This telephone contact will be timed to occur when the participant is due to receive the first *Stop Smoking for Good* booklet. The aim of this 10-minute call will be to build rapport and to provide a personal connection to garner trust and credibility in the intervention. During the call, we will briefly present the rationale for the intervention and offer suggestions for intended use of the intervention materials. If effective, this intervention could blend seamlessly into existing telephone Quitline services.

**D3.3.2 Usual Care (UC).** This condition will comprise a single, high-quality booklet that is currently in wide-dissemination and was developed by the National Cancer Institute: *Viva de forma más*

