**Secondary Aim.** The secondary aim is to assess prospective moderators of the expected intervention effect (e.g., gender, SES, quitting motivation, nicotine dependence, *country of origin*, acculturation, *trait affect*, self-efficacy). Each moderator will be assessed individually within a logistic regression for the 24-month assessment and within a GEE model by adding the moderator and the interaction term for the moderator and condition. The GEE models will also include interaction terms for the moderator with time and with the time x condition interaction.

Significant interaction terms in a GEE model will be further explored using time-specific analyses. Significant interaction terms for the logistic regression at 24 months will be explored by assessing condition differences for each level of categorical moderators.

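### Use of the Internet option and preferences collected at follow-up are planned as moderators although they can arise after allocation, so their interactions with condition are not protected by randomisation

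*Combined protocol and SAP*

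**What the plan says.** Section D3.3 offers the electronic format to everyone: "participants in both conditions will have the option to also receive electronic versions via a link to a website". Section C.7.1 then says "we will track use of the Internet option and include it as an exploratory moderator variable in analyses". The metadata it describes are "how many times the link was accessed, and whether the electronic booklet(s) were downloaded". It adds: "We will also collect evaluations and preferences regarding internet distribution at follow-up to test as potential moderators or mediators of treatment effects".

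The two arms have different things to open. For Usual Care (UC), D3.3.2 says "This condition will comprise a single, high-quality booklet". For SS-SP, D3.1 describes "a series of 11 booklets distributed over 18 months, plus additional monthly contacts via 9 supportive pamphlets", which is 11 + 9 = 20 items. Table 2 marks 10 booklet months and 9 pamphlet months, or 19.

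Section D3.7.4 (Secondary Aim) tests each moderator one at a time, in the 24-month logistic regression and in the GEE model, by "adding the moderator and the interaction term for the moderator and condition". The GEE version also lets the moderator interact with time and with time by condition. Nothing there treats variables measured after allocation differently. The Secondary Aim's own moderators are baseline measures (D3.4.1).

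**The concern.** A condition-by-moderator interaction can be read as effect modification because randomisation balances the arms within each level of a variable fixed before allocation. Link accesses and downloads do not exist until materials have been sent, and follow-up preferences are formed on whatever the arm supplied. In UC, being a user means having opened a single booklet. In SS-SP it can mean returning to new material for 18 months, which plausibly goes with staying motivated to quit. If so, users in the two arms are different kinds of smoker, and so are non-users, and a comparison of arms within either group mixes the effect of the intervention with that selection.

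At stake is the reading of a secondary, exploratory result: whether the intervention appears to work better or worse among people who use the Internet version.

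**Working it through.** **Inputs from the plan (D3.7.2, D3.2).** 24-month abstinence 19.8% in UC and 28.8% in SS-SP; two-sided alpha 0.05; 700 per arm. Overall odds ratio: (0.288/0.712)/(0.198/0.802) = 1.64.

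**The plan's own figure.** It states 365 per group for the 24-month logistic regression. The usual two-proportion formula (pooled variance, 80% power) gives 356, which is 9 or 2.5% lower; a Wald calculation on the log odds ratio gives 360. The stated figure is adequately reproduced and is not in dispute. The plan gives no figure for the moderator analysis, so what follows is an illustration under assumptions.

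**Assumed model, with no true modification.** Unmeasured motivation u is standard normal.
- Abstinence: logit P = a(arm) + b·u, with a(arm) set to give 19.8% and 28.8%. The arm effect on the logit scale is the same at every u and does not involve use.
- Use: logit P = c(arm) + g(arm)·u, with c(arm) set to give the assumed share of users, m(arm).
- Abstinence among users = E[P(use|u)·P(abstinent|u)]/m; among non-users, E[(1 − P(use|u))·P(abstinent|u)]/(1 − m).
- Interaction ratio R = OR in users / OR in non-users.
- Var(ln R) = sum over the four arm-by-use cells of 1/[700·share·p·(1 − p)]; rejection rate = Φ(z − 1.96) + Φ(−z − 1.96), with z = |ln R|/SE.

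| Scenario | b | g UC / SS-SP | Users UC / SS-SP | OR users | OR non-users | R | Rejection |
|---|---|---|---|---|---|---|---|
| A. Same link to motivation, same share | 0.5 | 0.5 / 0.5 | 30% / 30% | 1.64 | 1.64 | 1.00 | 5% |
| B. Same link, different share | 1.0 | 1.5 / 1.5 | 10% / 50% | 1.00 | 1.12 | 0.90 | 6.4% |
| C. Linked only in SS-SP | 0.5 | 0 / 1.0 | 30% / 30% | 2.16 | 1.44 | 1.50 | 31% |
| D. As C, stronger motivation effect | 1.0 | 0 / 1.0 | 30% / 30% | 2.66 | 1.29 | 2.06 | 76% |

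**Scenario C in full.** Abstinence among users is 34.7% in SS-SP and 19.8% in UC; among non-users, 26.3% and 19.8%. The variance terms are:
- SS-SP users: 1/(700·0.3·0.347·0.653) = 0.0210
- SS-SP non-users: 1/(700·0.7·0.263·0.737) = 0.0105
- UC users: 1/(700·0.3·0.198·0.802) = 0.0300
- UC non-users: 1/(700·0.7·0.198·0.802) = 0.0129

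They sum to 0.0744, so SE = 0.273. With ln 1.496 = 0.403, z = 1.48 and the rejection rate is 0.31, against a nominal 0.05.

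**Range.** Over all scenarios run in which use differed between arms, R lay between 0.90 and 2.57 and false rejection between 5% and 93%. In B the interaction test is close to nominal, yet a true overall odds ratio of 1.64 shrinks to 1.00 and 1.12 within the two groups. If use is unrelated to motivation in both arms, both groups show 1.64 whatever the shares of users.

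**The case against.** Several points on the other side are sound.

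- **The bias is conditional.** A reader might infer that about 20 items against one is enough to bias the comparison. It is not. A different share of users creates no prognostic imbalance unless use is related to prognosis, and the large spurious interactions need that relation to differ between arms. The documents report neither the shares nor the relation. What remains is that the differing materials and duration give no reason to assume the favourable case.
- **The moderator is loosely defined.** Use of the Internet option might mean electing electronic copies rather than opening links; C.7.1 describes the metadata in a separate sentence. The timing of any election is not stated. An election recorded before allocation would be a legitimate moderator.
- **Mediation is legitimate.** The plan allows follow-up preferences to be tested as mediators, and a mediator necessarily arises after allocation. The point concerns only their use as moderators.
- **The analysis is labelled exploratory.** That moderates the strength of any claim and bears on multiplicity. It does not remove bias.
- **The Internet decision.** A reader might infer that a biased interaction would determine whether delivery moves fully online. C.7.1 says only that the information gathered should help with that choice. The information includes descriptive metadata and participants' evaluations, and no interaction test is named as the basis.

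**Conclusion.** The point holds as a minor one. Under the Secondary Aim model, link use and follow-up preferences entered as moderators give within-group effects and interactions that randomisation does not protect, and the plan has no separate handling for them. The size cannot be fixed from the documents. Under the assumed model it runs from nothing (scenario A) to odds ratios of 2.16 and 1.44 with about 31% false rejection (scenario C), and further if motivation matters more. These figures rest on an assumed standard normal motivation score, assumed slopes and assumed usage shares; only the abstinence rates and 700 per arm come from the plan.

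It would be wrong to extend this to the main result. The Aim 1 GEE and 24-month logistic analyses, the sample size and the power do not involve Internet use, and the baseline moderators of the Secondary Aim are not affected.

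**What to change.** Amend C.7.1 as follows.

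1. Restrict condition-by-moderator interactions to variables recorded before allocation. Include election of electronic copies only if it was recorded before allocation, and state when that was.
2. Do not fit condition-by-link-use or condition-by-follow-up-preference interactions.
3. Report link accesses, downloads and follow-up preferences descriptively by arm, or in a mediation analysis with its assumptions stated.

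The change is to wording and needs no new data. A new baseline question on the format of intervention materials is not a practical alternative. D3.4.1 shows that 12-month results were already in hand, and the mail or e-mail preference it mentions concerns assessment packets. The cost is that actual use is no longer examined as an effect modifier. If no election was recorded before allocation, no Internet-use variable of this kind would qualify for an interaction test. The acceptability data relevant to future Internet delivery are kept.
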